8.1.1 Adverse (Drug) Reaction

All noxious and unintended responses to a medicinal product related to any dose should be considered an adverse drug reaction. "Responses" to a medicinal product means that a causal relationship between a medicinal product and an AE is at least a reasonable possibility, ie, the relationship cannot be ruled out.

8.1.2 Unexpected Adverse Drug Reaction

An Unexpected Adverse Drug Reaction is defined as an adverse reaction, the nature or severity of which is not consistent with the applicable product information. For obicetrapib, the reference

safety information is included in the Investigator's Brochure currently in force. The reference safety information will be reviewed yearly and the periodicity of the review will be harmonized with the reporting period of the Development Safety Update Report.

8.1.3 Assessment of Adverse Events by the Investigator

The Investigator will assess the severity (intensity) of each AE as mild, moderate, or severe, and will also categorize each AE as to its potential relationship to study drug using the categories of yes or no.

Assessment of Severity

Mild – An event that is easily tolerated and generally not interfering with normal daily activities.

Moderate – An event that is sufficiently discomforting to interfere with normal daily activities.

Severe – An event that is incapacitating with inability to work or perform normal daily activities.

Causality Assessment

The relationship of an AE to the administration of the study drug is to be assessed according to the following definitions:

No (unrelated, not related, or unlikely to be related) – The time course between the administration of study drug and the occurrence or worsening of the AE rules out a causal relationship and another cause (concomitant drugs, therapies, complications, etc) is suspected.

Yes (possibly, probably, or definitely related) – The time course between the administration of study drug and the occurrence or worsening of the AE is consistent with a causal relationship and no other cause (concomitant drugs, therapies, complications, etc) can be identified.

The definition implies a reasonable possibility of a causal relationship between the event and the study drug. This means that there are facts (evidence) or arguments to suggest a causal relationship.

The following factors should also be considered:

• The temporal sequence from study drug administration-

The event should occur after the study drug is given. The length of time from study drug exposure to event should be evaluated in the clinical context of the event.

• Underlying, concomitant, intercurrent diseases-

Each report should be evaluated in the context of the natural history and course of the disease being treated and any other disease the patient may have.

Concomitant drug-

The other drugs the patient is taking or the treatment the patient receives should be examined to determine whether any of them might be recognized to cause the event in question.

• Known response pattern for this class of study drug-

Clinical and/or preclinical data may indicate whether a particular response is likely to be a class effect.

• Exposure to physical and/or mental stresses-

The exposure to stress might induce adverse changes in the recipient and provide a logical and better explanation for the event.

• The pharmacology and PK of the study drug-

The known pharmacologic properties (absorption, distribution, metabolism, and excretion) of the study drug should be considered.

Serious Adverse Events

An AE or adverse reaction is considered serious if, in the view of either the Investigator or Sponsor, it results in any of the following outcomes:

- Death;
- A life-threatening AE;

Note: An AE or adverse reaction is considered "life-threatening" if, in view of either the Investigator or Sponsor, its occurrence places the patient at immediate risk of death. It does not include an event that, had it occurred in a more severe form, might have caused death.

• Requires hospitalization or prolongation of existing hospitalizations;

Note: Any hospital admission with at least 1 overnight stay will be considered an inpatient hospitalization. An emergency room or urgent care visit without hospital admission will not be recorded as an SAE under this criterion, nor will hospitalization for a procedure scheduled or planned before signing of informed consent, or elective treatment of a pre-existing condition that did not worsen from baseline. However, unexpected complications and/or prolongation of hospitalization that occur during elective surgery should be recorded as AEs and assessed for seriousness. Admission to the hospital for social or situational reasons (ie, no place to stay, live too far away to come for hospital visits, or respite care) will not be considered inpatient hospitalizations.

- A persistent or significant disability/incapacity or substantial disruption of the ability to conduct normal life functions;
- A congenital anomaly/birth defect; or
- An important medical event.

Note: Important medical events that do not meet any of the above criteria may be considered an SAE when, based upon appropriate medical judgment, they may jeopardize the patient and may require medical or surgical intervention to prevent one of the outcomes listed above. Examples of such medical events include allergic bronchospasm requiring intensive treatment in an emergency room or at home, blood dyscrasias or convulsions that do not result in inpatient hospitalizations, or the development of drug dependency.

Serious Adverse Event Reporting – Procedures for Investigators

Initial Reports

All SAEs occurring from the time of the first dose of study drug until 30 days following the last administration of study drug must be reported to within 24 hours of the knowledge of the occurrence. After the 30-day reporting window, any SAE that the Investigator

considers related to study drug must be reported to Sponsor/designee.
To report the SAE, complete the paper SAE report form and forward the form by fax or email to at a graph or call the sAE reporting line (phone number listed below), within 24 hours of awareness. Simultaneously, the investigator must record the SAE and any additional information on the relevant source documentation/eCRF, as appropriate.
The Sponsor/designee or Investigator will report the SAEs through the web portal ToetsingOnline to the accredited IEC that approved the protocol, within 7 days of first knowledge for SAEs that result in death or are life threatening followed by a period of maximum of 8 days to complete the initial preliminary report. All other SAEs will be reported within a period of maximum 15 days after the Sponsor/designee or Investigator has first knowledge of the serious adverse events.
Safety Contact Information: SAE reporting line – Europe: Telephone: Fax: Email:
Follow-up Reports
The Investigator must continue to follow the patient until the SAE has subsided or until the condition becomes chronic in nature, stabilizes (in the case of persistent impairment), or the patient dies.
Within 24 hours of receipt of follow-up information, the Investigator must update the paper SAE form and submit any supporting documentation (eg, patient discharge summary or autopsy reports) to via fax or email. Simultaneously, the investigator must record the updates and any additional information on the relevant source documentation/eCRF, as appropriate.
Pregnancy Reporting
If a patient becomes pregnant during the study or within the safety follow-up period defined in the protocol, the Investigator is to stop dosing with study drug immediately and the patient should be withdrawn from the study. Early termination procedures should be implemented at that time.
A pregnancy is not considered to be an AE or SAE; however, it must be reported to within 24 hours of knowledge of the event. provide the Investigator/site the Exposure In Utero (EIU) form for completion. The Investigator/site must complete the EIU form and fax/email it back to
If the female partner of a male patient becomes pregnant while the patient is receiving study drug or within the safety follow-up period defined in the protocol, the Investigator should notify

The pregnancy should be followed until the outcome of the pregnancy, whenever possible. Once the outcome of the pregnancy is known, the EIU form should be completed and faxed/emailed to

as described above.

If the outcome of the pregnancy meets the criteria for immediate classification as an SAE (ie, postpartum complication, spontaneous abortion, stillbirth, neonatal death, or congenital anomaly), the Investigator should follow the procedures for reporting an SAE.

Expedited Reporting

The Sponsor/designee will report all relevant information about Suspected Unexpected Serious Adverse Reactions (SUSARs) that are fatal or life-threatening as soon as possible to the applicable competent authorities in all the Member States concerned and to the Central Ethics Committee, and in any case no later than 7 days after knowledge by the Sponsor/designee of such a case. Relevant follow-up information will subsequently be communicated within an additional 8 days.

All other SUSARs will be reported to the applicable competent authorities concerned and to the Central Ethics Committee concerned as soon as possible but within a maximum of 15 days of first knowledge by the Sponsor/designee.

The Sponsor/designee will also report any additional expedited safety reports required in accordance with the timelines outlined in country-specific legislation.

The Sponsor/designee will also inform all Investigators as required per local regulation.

The requirements above refer to the requirements relating to investigational medicinal product.

Special Situation Reports

Special situation reports include reports of overdose, misuse, abuse, medication error, and reports of adverse reactions associated with product complaints.

- Overdose: Refers to the administration of a quantity of a medicinal product given per administration or cumulatively (accidentally or intentionally), which is above the maximum recommended dose according to the protocol. Clinical judgment should always be applied. In cases of a discrepancy in the drug accountability, overdose will be established only when it is clear that the patient has taken additional dose(s) or the Investigator has reason to suspect that the patient has taken additional dose(s).
- **Misuse:** Refers to situations where the medicinal product is intentionally and inappropriately used in a way that is not in accordance with the protocol instructions or local prescribing information and may be accompanied by harmful physical and/or psychological effects.
- **Abuse:** Is defined as persistent or sporadic, intentional excessive use of a medicinal product, which is accompanied by harmful physical or psychological effects.
- **Medication error:** Is any unintentional error in the prescribing, dispensing, or administration of a medicinal product by a healthcare professional, patient, or consumer, respectively. The administration or consumption of the unassigned treatment and administration of an expired product are always reportable as medication errors; cases of patients missing doses of investigational product are not considered reportable as medication errors.
- **Product complaint:** Is defined as any written, electronic, or oral communication that alleges deficiencies related to the identity, quality, durability, reliability, safety, effectiveness, or performance of a drug or device after it is released for distribution. A special situations report form will only be completed if a complaint is associated with an adverse drug reaction.

All special situation events as describ	bed above must be reported on the special situations report
form and faxed/emailed to	contact information listed below) within
24 hours of knowledge of the event. A	All AEs associated with these special situation reports should
be reported as AEs or SAEs as well	as recorded on the AE eCRF and/or the SAE report form.
Details of the symptoms and signs, clavailable.	linical management, and outcome should be provided, when

Safety Contact Information:
SAE reporting line – Europe:
Telephone:
Fax:
Email:

Clinical Laboratory Evaluations

Blood for chemistry and hematology will be obtained as indicated in Appendix A and sent to a central laboratory for analysis. See Appendix B for a complete list of analytes. Blood samples for chemistry and hematology must be obtained under fasting conditions (ie, after the patient has fasted for ~10 hours). For the purposes of this study, fasting will be defined as nothing by mouth except water and any essential medications. If a patient is not fasting, the Investigator will reschedule the visit as soon as possible. eGFR will be calculated using the Chronic Kidney Disease Epidemiology Collaboration equation (see Appendix B). At the Screening Visit only, the hematology panel will include HbA1c and APOE E4 genotyping. At the Screening Visit only, the chemistry panel will include TSH, T3, T4, folic acid, and vitamin B12.

Urine will be obtained as indicated in Appendix A and sent to a central laboratory for complete urinalysis. See Appendix B for a complete list of analytes.

An FSH test and urine pregnancy test will be performed at the Screening Visit prior to participation in the study for women <55 years of age for whom it has been ≥1 year since their last menstrual period. Urine pregnancy test will be repeated at EOT/ET Visit (V6).

Vital Signs

Vital signs will be taken as indicated in Appendix A. Vital signs will include body temperature, heart rate, and triplicate blood pressure (systolic and diastolic) measurements.

Height and weight will be measured at the Screening Visit and will be used to calculate body mass index. Weight only will be measured at the EOT visit as indicated in Appendix A. Measurement of weight should be performed with the patient dressed in indoor clothing, with shoes removed, and bladder empty.

Electrocardiograms

A single, standard 12-lead ECG will be performed by the Investigator or trained site personnel at the Screening Visit. and at the EOT visit

Physical and Neurological Examinations

Physical and neurological examinations will be performed as indicated in Appendix A.

Magnetic Resonance Scan

Magnetic resonance imaging of the brain will be performed at Screening and as clinically indicated (only in patients without historical MRI available within 6 months of the Screening Visit). This technology will be used to check for evidence of clinically relevant inclusion/exclusion and safety findings.

The MRI scans will be reviewed by the investigator or qualified designee for immediate patient management. Any clinically significant findings noted at Screening that result in a diagnosis should be recorded as a preexisting condition or AE.

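### The yes/no causality definitions for adverse events are not exhaustive, and the Yes condition contradicts both its own label and the standard in Protocol 8.1.1

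*Protocol*

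**What the plan says.** Protocol 8.1.3 has the investigator judge each adverse event's relationship to study drug "using the categories of yes or no", according to two definitions printed under Causality Assessment.

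- The negative category opens "No (unrelated, not related, or unlikely to be related". Its text requires that the time course "rules out a causal relationship and another cause (concomitant drugs, therapies, complications, etc) is suspected".
- The positive category opens "Yes (possibly, probably, or definitely related". Its text requires that the time course "is consistent with a causal relationship and no other cause (concomitant drugs, therapies, complications, etc) can be identified".

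After the definitions comes a remark that a reasonable possibility of causation is implied, with the explanation: "This means that there are facts (evidence) or arguments to suggest a causal relationship". A list of factors to consider follows: temporal sequence, other diseases, concomitant drugs, class effects, stress, and the drug's pharmacology.

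Protocol 8.1.1 defines an adverse drug reaction separately. A response counts when a causal relationship "is at least a reasonable possibility, ie, the relationship cannot be ruled out".

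**The concern.** Each definition joins two conditions with 'and', and no default is given for an event that meets one condition of each. The mixed case is foreseeable. Patients are 50 to 75 years old with Alzheimer's disease, may stay on stable Alzheimer's medication and on low-dose aspirin or clopidogrel, and undergo lumbar punctures. The Protocol's Risk/Benefit section also describes two patients in earlier studies whose severe events were suspected to be related to both obicetrapib and a concomitant statin. Lipid-altering therapy is excluded here, so that pairing should not recur, but it shows that dual attribution has arisen in this programme.

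At stake is consistent recording of relatedness. In an open-label, single-arm study no control rate helps to attribute events, so individual causality judgements carry more weight. Under the Protocol's section on serious adverse event reporting, relatedness decides whether a serious event more than 30 days after the last dose must be reported. It also supplies the 'suspected' element of suspected unexpected serious adverse reactions, which have 7-day and 15-day deadlines under Expedited Reporting.

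**Working it through.** There is no figure in the plan to reproduce. The check is to cross the conditions in the two 8.1.3 definitions and see which combinations are assigned.

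**Step 1. Timing (2 levels) by other cause (2 levels), giving 2 × 2 = 4 combinations.**

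| Timing | Other cause | Meets Yes? | Meets No? | Result |
|---|---|---|---|---|
| Consistent | None | Yes | No | Yes |
| Consistent | Identified | No: another cause is identified | No: timing does not rule causation out | Neither |
| Ruled out | None | No: timing | No: no other cause suspected | Neither |
| Ruled out | Suspected | No: timing | Yes | No |

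Two of four combinations are defined.

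**Step 2. Respect the difference in wording.** The Yes text speaks of a cause being identified, the No text of one being suspected. Splitting other cause into three levels gives 2 × 3 = 6 combinations.

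| Timing | None | Suspected only | Identified |
|---|---|---|---|
| Consistent | Yes | Yes | Neither |
| Ruled out | Neither | No | No |

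Four of six are defined. Both gaps remain, but the gap under consistent timing is confined to causes that can be identified.

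**Step 3. Compare with 8.1.1.** Take an event with consistent timing and an identifiable alternative. Unless that alternative excludes the drug, the relationship cannot be ruled out, so 8.1.1 makes the event a reaction. It fails the literal Yes text of 8.1.3, which is therefore the stricter test. The other gap gives no such conflict: timing that rules causation out also means the event is not a reaction under 8.1.1.

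**Step 4. Compare the Yes text with its own label.** The label admits events that are only possibly related. The text admits an event only when no other cause can be identified. An event with two candidate causes is a natural case of a possible relationship, yet the text shuts it out.

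**Step 5. See whether the text that follows closes the gap.** The reasonable-possibility remark interprets the definition; it does not withdraw the condition about other causes. It also explains the phrase by positive evidence, where 8.1.1 explains it by inability to rule the relationship out. The factors are to be considered, but none is tied to a category. Neither element assigns the mixed case.

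**The case against.** The strongest reply is that an experienced investigator would not apply the definitions as strict logical tests. The Yes label, the reasonable-possibility remark and 8.1.1 all lean towards Yes for a mixed case. The factor list asks for competing causes to be weighed, which would be pointless if any alternative disqualified an event. In the other gap, excluded timing points plainly to No. This stands as a reason to expect sensible practice. It does not stand as a reading that resolves the text: 8.1.3 tells the investigator to assess according to the definitions, and they conflict with the surrounding guidance.

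The second reply is that little depends on the answer, and much of this stands.

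- All serious events from first dose to 30 days after the last dose are reported within 24 hours, and serious events also go to the ethics committee, with no causality filter.
- For a patient dosed to Day 168, the 30-day window ends at 168 + 30 = Day 198, the nominal day of the last contact. The causality filter therefore mostly operates after scheduled contact has ended.
- Reporting of suspected unexpected serious reactions is the duty of the sponsor or its designee. No passage makes it depend solely on the investigator's yes/no answer.
- Neither Protocol 9.1.2 nor SAP 3.6 specifies a summary of related events, and no inference is applied to safety data.

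A reader might infer that any alternative cause, or simply having a comorbidity or taking another drug, keeps an event out of Yes. The text does not say that: a merely suspected alternative still satisfies the Yes definition, and a comorbidity is not thereby identified as the cause of a given event.

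**Conclusion.** The rule is wrong as written. Two of four combinations are assigned (four of six when suspected and identified causes are separated), and the Yes condition contradicts both its label and 8.1.1. The consequence is inconsistent classification, with a risk that some possible reactions are not recorded as related. This rests on a literal reading; the documents contain no form-completion guidance that would show actual practice.

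Two stronger conclusions are tempting and unsupported. One is that related events will be understated. The mixed case cannot literally be No either, so it is unassigned, and understatement is a risk rather than a result. The other is that the unassigned combination is the commonest one in this age group. The documents give no frequencies, and the exclusion criteria remove many comorbidities and concomitant drugs.

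The practical effect in 10 to 15 patients is limited, because no specified table changes and serious events within the 30-day window are reported regardless. It is not nil: later serious events and the 'suspected' element of expedited reporting still use the judgement. The correction is worth making because it costs almost nothing and uses a standard the protocol already contains.

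**What to change.** Reconcile 8.1.1 and 8.1.3 under one standard, so that the two categories are complements:

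- Yes: there is a reasonable possibility that study drug caused the event, that is, a causal relationship cannot be ruled out, whether or not another cause is also possible.
- No: there is no reasonable possibility that study drug caused the event.

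Keep the listed factors as guidance for reaching that judgement, and align the explanation of reasonable possibility in 8.1.3 with the one in 8.1.1. Every combination in the tables then falls in exactly one category.

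The cost is two sentences in the protocol and matching guidance for the adverse event form. The downside is that the count of related events may rise slightly.

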9 STATISTICS

A statistical analysis plan (SAP) will be written. The SAP will provide full details of the analyses and data displays. In case of discrepancies in statistical analyses described in the protocol versus the SAP, the SAP will prevail.

Analysis Populations

The Intent-to-Treat (ITT) Population will include all patients who receive at least 1 dose of study drug.

The Per-Protocol (PP) Population will include all patients who have a study drug compliance percentage of at least 80% over the entire study duration. The PP Population will be the primary population used for the PD and PK analyses, and for the analyses of the effects of obicetrapib on cognition.

The Safety Population will include all patients who receive at least 1 dose of study drug. The Safety Population will be the primary population used for the safety analyses.

Statistical Methods

All study-collected data will be summarized by treatment group using descriptive statistics, graphs, and/or raw data listings. Descriptive statistics for continuous variables will include number of patients (n), mean, standard deviation (SD), median, minimum, and maximum values. Analysis of categorical variables will include frequency and percentage.

No formal hypothesis will be tested in this study.

